11.4 Adherence to the Protocol	22
11.5 Amendments to the Protocol.....	23
11.6 Confidentiality.....	23
11.7 Provisions to Protect the Privacy Interests of Subjects	23
11.8 Record Retention	24
11.9 Obligations of Investigators.....	24
12.0 REFERENCES	24
13.0 APPENDIX 1: Pill Diary	27

[figure not shown]
LIST OF ABBREVIATIONS

AE	Adverse Event
ALC	Absolute Lymphocyte Count
ALT	Alanine Aminotransferase
AST	Aspartate Aminotransferase
BAT	Basophil Activation Test
BTK	Bruton's Tyrosine Kinase
BUN	Blood Urea Nitrogen
CBC	Complete Blood Count
CLL	Chronic Lymphocytic Leukemia
CMP	Comprehensive Metabolic Panel
CRU	Clinical Research Unit
SBPC	Single-blind Placebo-controlled
DLT	Dose-Limiting Toxicity
DSMB	Data and Safety Monitoring Board
EKG	Electrocardiogram
FC	Food Challenge
H&P	History & Physical Exam
HRPP	Human Research Protections Program
IgE	Immunoglobulin E
IV (or iv)	Intravenously
MCL	Mantle Cell Lymphoma
MTD	Maximum Tolerated Dose
OFC	Oral Food Challenge
PBMCs	Peripheral Blood Mononuclear Cells
p.o.	per os/by mouth/orally
PST	Peripheral Blood Testing
SAE	Serious Adverse Event
sIgE	Surface Immunoglobulin E
SGOT	Serum Glutamic Oxaloacetic Transaminase
SPGT	Serum Glutamic Pyruvic Transaminase
SPT	Skin Prick Test
WBC	White Blood Cells
WM	Waldenstrom's Macroglobulinemia

[figure not shown]
This is a phase II open label study on the use of Ibrutinib on the inhibition of food-induced anaphylaxis in adults with food allergy. Ibrutinib (brand name Imbruvica) is currently FDA approved for the treatment of mantle cell lymphoma (MCL), chronic lymphocytic leukemia (CLL), and Waldenstrom's macroglobulinemia (WM). We propose to administer this approved drug to adults with food allergy to inhibit anaphylaxis.

STUDY SCHEMA

This is open-label study consists of 2 parts. Part 1 is designed to determine the fewest doses and shortest length of time, from two days to up to 7 days, needed for ibrutinib to fully inhibit tests for food allergy, and to determine the length of persistence of efficacy after the drug is stopped. Part 2 is designed to determine the ability of ibrutinib, optimally dosed as defined in Part 1, to prevent signs and symptoms of anaphylaxis during a food challenge in food-allergic subjects.

for toxicities (see below). After this visit, subjects will be given ibrutinib (two doses of 420 mg of ibrutinib to start the following day and to be taken orally at 8am exactly 24 hours apart) and return for **Visit 2** to undergo repeat PST and phlebotomy for testing preformed in an identical manner to Visit 1. If two consecutive doses of 420 mg of ibrutinib given 24 hours apart is insufficient to cause >80% inhibition of the SPT and BAT response, subjects will be given two additional doses of 420 mg of ibrutinib to continue to take at 8am exactly 24 hours apart for two more days, and return for **Visit 3** for identical repeat testing as in Visits 1 and 2. If four consecutive doses of 420 mg of ibrutinib given 24 hours apart is insufficient to cause >80% inhibition of the SPT and BAT response, subjects will be given three additional doses of 420 mg of ibrutinib to continue to take 24 hours apart for three more days, and return for **Visit 4** for identical repeat testing as in Visits 1, 2 and 3, where based on preliminary data, we expect SPT and BAT to be suppressed. Once both the SPT and BAT responses are inhibited, no further ibrutinib doses will be given, and subjects will return on a weekly basis until both the peanut/tree nut PST and BAT return to at least 80% of baseline values. At this point, Part 1 will have been completed. At each visit, patients will be monitored for toxicities, including CBC, CMP, and pregnancy testing. Prior to drug initiation and at the end of the trial, an EKG will be performed.

Clinical protocol for part 1 (top) and part 2 (bottom). * or - = predicted response; ??? = question to be answered; * = if needed

and subjects will return on a weekly basis until both the peanut/tree nut PST and BAT return to at least 80% of baseline values. At this point, Part 1 will have been completed. At each visit, patients will be monitored for toxicities, including CBC, CMP, and pregnancy testing. Prior to drug initiation and at the end of the trial, an EKG will be performed.

Part 2: Visit 1 will be identical to those for Part 1 except that subjects will take a higher dose of ibrutinib (560mg daily) for 2 days and a single-blind, placebo-controlled (SBPC) graded food challenge of up to 8 mg of peanut or tree nut protein, administered over escalating doses, will be performed in a monitored at the study site in a clinical research unit (CRU) setting. Prior to the SBPC food challenge, 30 mL of peripheral blood will be collected for BAT, sIgE to peanut and components, as well as for total IgE, eosinophil and basophil enumeration. During the challenge, subjects will be repeatedly assessed for signs and symptoms of food-induced anaphylaxis between each dose per food challenge protocol. This visit will establish each subject's baseline threshold dose for peanut/tree nut reactivity.

Once a confirmed reaction occurs, the food challenge will be terminated and the reaction treated until it has resolved. Within 15 minutes of a positive challenge, an additional 10 mL of blood will be drawn for mast cell microparticle analysis. After a minimum of a two week recovery period, each subject will then begin taking ibrutinib 560 mg orally daily for 2 days, which is the minimum number of doses that

demonstrate efficacy as determined in Part 1. Two hours after the final dose, subjects will return to the study site for **Visit 2**, and PST and SBPC food challenges will be repeated to establish each subject's new threshold dose for peanut/tree nut reactivity while on ibrutinib, and with repeat post-challenge blood collection for mast cell microparticle analysis. At this point of the protocol, ibrutinib dosing will be stopped. Follow up visits starting 3 months after cessation of ibrutinib will be conducted to repeat toxicity labs and skin testing.

STUDY SUMMARY

Title	Inhibition of Anaphylaxis by Ibrutinib
Protocol Number	BB20150924
Phase	Phase 2
Methodology	Open label study to determine dosing and safety of Ibrutinib for the treatment of food allergy
Study Duration	12 weeks
Study Center(s)	Single-center
Objectives	
Primary: To determine the shortest amount of time and fewest ibrutinib doses required to eliminate food SPT and BAT reactivity and to evaluate the effect of pretreatment with ibrutinib on food allergen reactivity in food allergic subjects given ibrutinib 420 mg daily for 2-7 doses
 
Secondary: To determine if a suppressed SPT response to peanut, despite normal BAT responses, predicts whether a SBPC food challenge will be altered from baseline threshold dose for peanut reactivity.

Number of Subjects	12
Diagnosis and Main Inclusion Criteria	Adults with food-challenge proven food allergy to peanut (or tree nut)will be invited to participate.
Study Product(s), Dose, Route, Regimen	Ibrutinib 420 or 560 mg, PO once daily
Duration of administration	2-7 days
Reference therapy	There are currently no approved therapies for food allergy
Statistical Methodology	Descriptive statistics will be used to determine 80% reduction in allergy test size (skin testing) and basophil degranulation during treatment.

1.0 BACKGROUND AND RATIONALE

1.1 Disease Background

Food allergy is a potentially life threatening disease, and its prevalence continues to increase despite public health efforts (1,2). Newer studies have shown that it is less likely that a subject will lose their food allergies over time and food allergies can also start in adulthood, so more adults now have life-threatening food allergies. Near fatal and fatal reactions can occur of subjects with food allergies and can lead to devastating results (3,4). Furthermore, the economic burden of childhood food allergy is nearly \$25 billion per year, including 200,000 emergency department trips annually (5). Despite this significant disease burden, there are currently no approved therapies for food allergy. Standard of care is constant vigilance in avoidance of allergen, and use of self-injected epinephrine after a reaction has occurred. Therefore, there is a large unmet need for new therapeutics to prevent serious allergic disease including food allergy and anaphylaxis. Newly FDA approved BTK inhibitors such as ibrutinib (as well as others under development (6,7)) may be able to fill this void, and offer a therapy to these subjects.

1.2 Study Drug Background and Associated Known Toxicities

Ibrutinib is a once daily, oral, selective, irreversible small-molecule inhibitor of Bruton's tyrosine kinase (BTK), a key component of B-cell receptor signaling (8,9). BTK is also essential for Fc ϵ RI signaling and triggering of mast cells and basophils (10){Iyer, 2011 #10272;Kuehn, 2008 #10273;MacGlashan, 2011 #8797}. It is currently FDA approved for the treatment of Mantle Cell Lymphoma (MCL), Chronic Lymphocytic Leukemia (CLL) and Waldenstrom's macroglobulinemia (WM).

In subjects with recurrent B-cell lymphoma, >90% irreversible occupancy of the BTK active site in peripheral blood mononuclear cells was observed up to 24 hours after ibrutinib doses of \geq 2.5 mg/kg/day. Ibrutinib is absorbed with a median Tmax of 1-2 hours. It is metabolized by cytochrome P450 and CYP3A, and has a half-life of 4-6 hours. The majority (80%) is fecally excreted.

The approved CLL and WM dose (420 mg orally once daily) has been shown to inhibit allergy test responses in cancer subjects receiving this drug by 1 week of treatment (the earliest time point examined) in preliminary data from our group. The 560 mg dose (used for MCL) has similar side-effect and toxicity profiles as the lower dose. Initial data from Part 1 suggests that the 420mg dose can at least partially (in some cases fully) inhibit skin test responses to peanut and tree nuts in allergic subjects after just 2 doses, with minimal side effects and no observed toxicity thus far in subjects taking ibrutinib for up to 7 days. Therefore, we can justify using the higher dose of 560 mg orally once daily for Part 2 to investigate whether this higher dose can further reduce skin test responses beyond what is seen with the lower dose.

In human studies, ibrutinib is metabolized in the liver, and not significantly renally cleared. In healthy volunteers, co-administration with CYP3A inhibitors increased Cmax, and therefore the drug will not be concomitantly administered with strong or moderate inhibitors of CYP3A. Known toxicities in cancer subjects receiving ibrutinib chronically include bleeding events (5% of MCL subjects), infection (25% of MCL subjects), myelosuppression (41% of subjects), and renal toxicity has also been reported. Ibrutinib is also pregnancy category D. This underscores our goal of finding the fewest possible doses to achieve the anti-allergy effect we are seeking, which could be as few as just 2 doses.

1.3 Rationale

There are currently no treatments for food allergy. IgE uniquely arms mast cells and basophils via their surface expression of Fc ϵ RI in allergy. Crosslinking of the receptor is known to activate a number of SRC-family kinases (e.g., LYN, SYK) required for receptor function. BTK is a key

component of Fc ϵ RI signaling and triggering of mast cells and basophils. Since signaling mediated by Fc ϵ RI aggregation is thought to require the activity of BTK (8,9), MacGlashan et. al. (9) tested ibrutinib, formerly known as PCI-32765, for its ability to prevent activation of human basophils *in vitro*. For stimulation with anti-IgE, ibrutinib inhibited CD63, CD203c and CD11b upregulation, and release of histamine, LTC4 and IL-4 as well as the cytosolic calcium response (IC₉₀ of \approx 50 nM). Ibrutinib did not inhibit basophil activation by FMLP or C5a and did not inhibit IL-13 release induced by IL-3, suggesting that BTK is required for IgE-mediated activation of human basophils. We propose to test whether this pharmacology can be exploited *in vivo* to prevent allergic reactions.

Peanut and tree nut allergies are among the most common adult food allergens, and can often be the most severe. Additionally, peanut and tree nut allergies are often life-long. Young adults and adolescents have a higher rate of accidental exposure and mortality as a result of food allergies than younger children, so there is an unmet need for therapies directed at food allergy, especially in this population. Therefore, we have chosen peanut and tree nut allergies in an effort to investigate a treatment that has the potential to benefit the most individuals with a potentially severe allergy.

2.0 STUDY OBJECTIVES

2.1 Primary Objective

- 2.1.1 To determine if short term administration of ibrutinib to adults with peanut (or tree nut) allergy will safely change allergen challenge thresholds

2.2 Secondary Objectives

- 2.2.1 To describe the adverse events associated with ibrutinib when administered in a short course of 2-7 doses daily
- 2.2.2 To determine the minimum number of doses of ibrutinib needed to inhibit testing for food allergy (SPT and BAT)
- 2.2.3 To determine the length of effect of inhibition of testing for food allergy after the drug is stopped (SPT and BAT)
- 2.2.4 To determine if 2-7 daily doses of ibrutinib have any impact on blood levels of total and food-specific IgE, and numbers of circulating eosinophils and basophils.

2.3 Endpoints

Primary Objective 2.1.1: The highest dose of food allergen that is tolerated in a food challenge prior to reaction occurring in a food challenge, both before and while taking ibrutinib.

Secondary Objective 2.2.1: Adverse events, including bleeding, hepatotoxicity and renal toxicity will be monitored.

Secondary Objective 2.2.3: Change in SPT size and percent activation of basophils from BAT will be determined.

Secondary Objective 2.2.4: Change in blood levels of total and food-specific IgE, and numbers of circulating eosinophils and basophils.

Exploratory Objective: Clinical signs and symptom of food allergy reactions will be compared among subjects at oral food challenge visit in the study.

3.0 SUBJECT ELIGIBILITY

Subjects must meet all of the inclusion and exclusion criteria to be enrolled in the study. Study procedures may not begin until a subject signs the informed consent form.

3.1 Inclusion Criteria

- 3.1.1 History of food allergy to peanut (or tree nut).
- 3.1.2 Male or female age \geq 18 years.
- 3.1.3 Positive skin prick testing and basophil activation test to the trigger food(s), either peanut and/or tree nut(s).
- 3.1.4 Clinical reaction to oral food challenge at baseline (for Part 2 only)
- 3.1.5 Adequate organ and marrow function as defined below:

- leukocytes	\geq 3,000/mcL
- absolute neutrophil count	\geq 1,500/mcL
- platelets	\geq 100,000/mcL
- total bilirubin	within normal institutional limits
- AST(SGOT)/ALT(SPGT)	within normal institutional limits
- Creatinine	within normal institutional limits
- 3.1.6 Women of child bearing potential must agree to two forms of highly effective contraception (hormonal, device, or barrier method of birth control; abstinence) prior to study entry, for the duration of study participation, and for 90 days following completion of therapy. Should a woman become pregnant or suspect she is pregnant while participating in this study, she should inform the Principal Investigator and her treating physician immediately.
 - 3.1.5.1 A female of child bearing potential is any woman (regardless of sexual orientation, having undergone a tubal ligation, or remaining celibate by choice) who meets the following criteria:
 - Has not undergone a hysterectomy or bilateral oophorectomy; or
 - Has not been naturally postmenopausal for at least 12 consecutive months (i.e., has had menses at any time in the preceding 12 consecutive months).
- 3.1.7 Ability to understand and the willingness to sign a written informed consent.
- 3.1.8 Ability to clearly understand and speak English at an 8th grade reading level. For safety reasons, subjects must speak English due to the anticipated need for clear and timely communication with investigators and the study team in emergency situations, since the investigators and study team are English speaking.

3.2 Exclusion Criteria

- 3.2.1 Subjects who have been on immunomodulatory therapies or oral corticosteroids within 1 month prior to study participation will be excluded, and those taking antihistamines must stop these drugs for one week prior to enrollment and must refrain from taking antihistamines during the duration of the study so as not to interfere with SPT responses.
- 3.2.2 Subjects with symptoms not consistent with type 1 food reactions (atopic dermatitis, eosinophilic esophagitis and any other non-IgE-mediated food sensitivities) will be excluded.

- 3.2.3 History of allergic reactions attributed to compounds of similar chemical or biologic composition to ibrutinib.
- 3.2.4 Uncontrolled inter-current illness including, but not limited to, ongoing or active infection, symptomatic congestive heart failure, unstable angina pectoris, cardiac arrhythmia, beta-blocker use or psychiatric illness/social situations that would limit compliance with study requirements.
- 3.2.5 Subjects must not be pregnant or nursing due to the potential for congenital abnormalities and the potential of this regimen to harm nursing infants.
- 3.2.6 Subjects on anticoagulants, anti-platelet therapy, or any other predisposition towards bleeding.
- 3.2.7 Subjects with history of idiopathic urticaria, dermatographism, idiopathic or unexplained anaphylaxis, or anaphylaxis (to foods or otherwise) resulting in intubation, prolonged hypotension, or neurological sequelae

3.3 Study Stopping Criteria

The study will be stopped if >50% of patients cannot complete the protocol due to toxicities or adverse events. Toxicities (section 4.2) and adverse events (section 7.0) are listed below. Monitoring is described in section 8.0.

[figure not shown]
3.4 Recruitment

Patients with a diagnosis of peanut or tree nut allergy by a board certified allergist-immunologist will be identified as potential subjects from the allergy clinics at Northwestern University Feinberg School of Medicine. The treating physician will ask potential subjects permission to be contacted by study personnel. Potential subjects will then be contacted by authorized study personnel and given time to review the study information and consider participation.

4.0 TREATMENT PLAN

4.1 Treatment Dosage and Administration

For Part 1 of the study, we will determine the length of treatment (i.e., the number of daily doses) required to inhibit both basophil and food skin test responses. Preliminary data demonstrates that 7 days of treatment will inhibit both basophil and mast cell responsiveness to aeroallergens, but have not yet tested shorter time points. Prior studies in cancer subjects suggest that one dose is sufficient to completely inhibit BAT, but we propose a minimum of two doses to allow for diffusion and penetration of ibrutinib into the skin compartment where our SPT is performed to assess skin mast cell responsiveness. For Part 1, 6 subjects will take ibrutinib 420 mg, by mouth once daily (every 24 hours) on an outpatient basis. After two days, the subject will undergo blood testing and SPT to assess basophil and mast cell reactivity. If both tests are negative, Part 1 is completed. If both tests are not negative, then the subject will take 2 more days of ibrutinib (same dose, for a total of 4 doses), and identical testing will be repeated. If testing is not negative at day 4, the subject will take 3 more days of ibrutinib (same dose, for a total of 7 doses), which is the maximum anticipated number of doses needed to suppress both the BAT and SPT.

For Part 2 of the study, 6 subjects will take ibrutinib 560 mg once daily by mouth (every 24 hours) for 2 days, which is the minimum number of days required to cause $\geq 80\%$ inhibition of food SPT and BAT responses as determined in part 1. Part 2 will last a minimum of 3 days.

Dose-limiting toxicity (DLT) includes any grade 3 or 4 hematologic toxicity, grade 3 hepatotoxicity or increase in creatinine $\times 2.5$ normal limit. DLT will be monitored at each visit, at any time during treatment.

Maximally tolerated dose (MTD) will occur at the point DLT occurs. Ibrutinib is approved as a daily medication for another indication, and we propose to use the drug in adults only at its approved oral dosing of 420 or 560 mg daily for a minimum of two days and a maximum of 7 days. Dose limiting events include grade 3 or 4 hematologic events, grade 3 or 4 hepatotoxicity, AST or ALT >3 times normal range, creatinine >2.5 times normal range. DLT evaluation will be completed throughout the study, anytime during treatment.

In healthy volunteers, co-administration with CYP3A inhibitors increased C_{max} , and therefore the drug will not be concomitantly administered with strong or moderate inhibitors of CYP3A (for example, “azole” medications and subjects will be advised against drinking grapefruit juice).

4.2 Toxicities and Dosing Delays

Any subject who receives treatment on this protocol will be evaluable for toxicity. Each subject will be assessed for the development of toxicity according to the Time and Events table (Section 5.4).

At each visit, subjects will be monitored for toxicities. If a subject develops a grade 3 or 4 hematologic, renal, or hepatotoxicity, the medication will be stopped. Toxicities with grades are listed below.

Hematological Toxicities:

Hematological Toxicity Dose Reductions for Ibrutinib		
ANC	Platelets	Action
$\geq 1,500/\mu\text{L}$	100,000/μL	None.
1000-1499/ μL	75,000-99,000/μL	
-1st Occurrence: Hold current dose until ANC $\geq 1,500/\mu\text{L}$ and platelets $\geq 100,000/\mu\text{L}$. Do not replace missed doses. Restart next treatment at TBD dose.
 
-2nd Occurrence: Hold current dose until ANC $\geq 1,500/\mu\text{L}$ and platelets $\geq 100,000/\mu\text{L}$. Do not replace missed doses.

		-3rd Occurrence: Discontinue protocol therapy.
500-999/ μ L	50,000-74,000/μL	
-1st Occurrence: Hold current dose until ANC \geq 1,500/μL and platelets \geq 100,000/μL. Do not replace missed doses. Restart next treatment at TBD dose.
 
-2nd Occurrence: Hold current dose until ANC \geq 1,500/μL and platelets \geq 100,000/μL. Do not replace missed doses. Restart next treatment at TBD dose.
 
-3rd Occurrence: Discontinue protocol therapy.

<500/ μ L	<50,000/μL	
-1st Occurrence: Hold current dose until ANC \geq 1,500/μL and platelets \geq 100,000/μL. Restart next treatment at TBD dose.
 
-2nd Occurrence: Discontinue protocol therapy.

Renal Toxicity: Creatinine will be monitored per protocol. Creatinine levels >2.5 times the normal limit will result in discontinuation of protocol therapy.

Hepatotoxicity: Grade 3 hepatotoxicity, or an increase in AST or ALT >3 times upper limit of normal will result in discontinuation in protocol therapy.

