8.1 Definitions

8.1.1 Definition of Adverse Event

An adverse event (AE) is any untoward medical occurrence in a subject receiving study treatment and which does not necessarily have a causal relationship with this treatment. An AE can therefore be any unfavorable and unintended sign (including an abnormal laboratory finding), symptom, or disease temporally associated with the use of an experimental intervention, whether or not related to the intervention.

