8.1.2 Severity of Adverse Events

The severity of an AE is graded as follows:

Mild (grade 1): the event causes discomfort without disruption of normal daily activities.

Moderate (grade 2): the event causes discomfort that affects normal daily activities.

Severe (grade 3): the event makes the subject unable to perform normal daily activities or significantly affects his/her clinical status.

Life-threatening (grade 4): the subject was at risk of death at the time of the event.

Fatal (grade 5): the event caused death.

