10.1 Study Design/Study Endpoints

This is an open label study of ibrutinib in 12 food allergic adults to determine the shortest amount of time and fewest ibrutinib doses required to eliminate food SPT and BAT reactivity and to evaluate the effect of pretreatment with ibrutinib on food allergen reactivity in food allergic subjects given ibrutinib 420 or 560 mg daily for 2-7 doses. Given the nature of the study, it will be stopped if >50% of patients have a DLT at target enrollment.

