11.3 Data Management and Monitoring/Auditing

As has been done previously for the phase 1 study of ibrutinib (13), adverse events will be monitored throughout treatment and toxicities will be assessed using the National Cancer Institute Common Toxicity Criteria for AEs, with its latest version, currently version 4.03.

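### Section 4.2 tells staff both to stop ibrutinib for a grade 3-4 ANC or platelet count and to restart it at an undefined dose; the study-stopping rules in 3.3/8.3.3 and 10.1 also count different events

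*Combined protocol and SAP*

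**What the plan says.** **Subject level.** The text of 4.2 is unconditional: "If a subject develops a grade 3 or 4 hematologic, renal, or hepatotoxicity, the medication will be stopped". It then announces that "Toxicities with grades are listed below". The hematology table that follows has columns for ANC, platelets and action, and no grade. In each of its three abnormal rows, the first-occurrence action is to hold until ANC is at least 1,500 and platelets at least 100,000, then "Restart next treatment at TBD dose". The two milder rows add "Do not replace missed doses" at first occurrence; the lowest row does not. The renal and hepatic paragraphs of 4.2 both end protocol therapy once their limits are crossed.

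Section 4.1 makes any grade 3 or 4 hematologic toxicity a DLT and names only two daily doses, 420 and 560 mg. Section 4.6 treats doses missed because of toxicity as a DLT. For grading, 11.3 says "toxicities will be assessed using the National Cancer Institute Common Toxicity Criteria for AEs".

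**Study level.** Sections 3.3 and 8.3.3 stop the study when more than 50% of patients cannot complete the protocol because of toxicities or adverse events, with no time stated. Of the study, 10.1 says "it will be stopped if >50% of patients have a DLT at target enrollment".

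**The concern.** Two people following 4.2 correctly could treat the same subject in opposite ways: one ends ibrutinib, the other re-doses after the lowest blood counts in the table. Section 7.1.2 describes these subjects as generally healthy apart from food allergy, so the case for re-dosing after a severe cytopenia is weak. Section 11.4 requires conduct exactly as the protocol describes, which is impossible where two instructions conflict.

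At study level, whether a given subject counts toward stopping depends on which section is read.

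**Working it through.** The plan gives no figure on this point, so the check sets the instructions side by side and counts doses.

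**Step 1: text against table (4.2).**

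| ANC or platelets (per µL) | Text, if grade 3-4 | Table, 1st occurrence | Table, 2nd | Table, 3rd |
|---|---|---|---|---|
| 1,000-1,499 or 75,000-99,000 | stop | hold, restart at TBD | hold, no restart stated | discontinue |
| 500-999 or 50,000-74,000 | stop | hold, restart at TBD | hold, restart at TBD | discontinue |
| <500 or <50,000 | stop | hold, restart at TBD | discontinue | – |

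The grades are not shown, but the conflict does not depend on them. All three rows restart drug at first occurrence, so any row that is grade 3-4 is stopped by the text and restarted by the table. If grade rises as counts fall, the lowest row is grade 3-4 whenever any row is.

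**Step 2: the restart dose.** Neither 420 nor 560 mg is named as the restart dose, and no reduced level is defined. Tablets are 140 mg (9.1), so 140, 280 or 420 mg could be made up for a Part 1 subject; the plan does not choose.

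**Step 3: who can be affected.** In Part 2, both doses have been taken when the Visit 2 CBC is drawn, and dosing then ends. Nothing remains to restart. In Part 1, scheduled CBCs fall after doses 2, 4 and 7 (Study Schema and 5.5), and only subjects whose tests are not yet suppressed continue past dose 2.

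**Step 4: doses after a first lowest-row count in Part 1.**

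- Found at Day 2. Text: 0. Table: doses 3 and 4 are held; if recovery is seen on the Day 4 CBC, doses 5 to 7 follow, so 7 − 4 = 3.
- Found at Day 4. Text: 0. Table: the next scheduled CBC is at Day 7, when the course is over, so 0.
- The upper limits rise to 7 − 2 = 5 (Day 2) and 7 − 4 = 3 (Day 4) only if missed doses are replaced, on which the lowest row is silent, or if an unscheduled CBC shows recovery before the next dose.

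**Step 5: DLT status of a mild hold.** Entry requires ANC of at least 1,500 (3.1). A hold at 1,000-1,499 means missed doses, which 4.6 counts as a DLT whatever the grade, whereas 4.1 ties hematologic DLTs to grade 3 or 4.

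**Step 6: study-level rules.** A Part 2 subject with a laboratory DLT at Visit 2 has finished dosing and may complete: counted by 10.1, possibly not by 3.3/8.3.3. A subject who cannot complete because of an adverse event outside the DLT list, such as a severe food-challenge reaction, is counted by 3.3/8.3.3 but not clearly by 10.1. Section 4.6 narrows the gap by making toxicity dropouts DLTs, but does not close it.

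**The case against.** **Stopped may mean held.** The text would then agree with the table. But the renal and hepatic paragraphs of the same section end therapy, the text mentions no restart, and the restart dose is undefined on either reading.

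**The practical reach may be nil.** This largely stands. The Study Schema and 4.1 already describe two days as the Part 1 result, and 1.2 reports no observed toxicity so far with up to 7 days of drug. The documents do not say how many Part 1 subjects remain. Three further doses would need ANC to rise from below 500 to at least 1,500, or platelets from below 50,000 to at least 100,000, between Day 2 and Day 4. That is a ceiling, not an expected harm. Sections 4.4 and 5.6 let the investigator discontinue drug or remove a subject for toxicity, and so decline the restart.

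**Is the grading scale ambiguous?** A reader might infer so, because 8.1.1 includes laboratory findings among adverse events ("any unfavorable and unintended sign (including an abnormal laboratory finding") and 8.1.2 grades by function ("Severe (grade 3): the event makes the subject unable to perform normal daily activities or significantly affects his/her clinical status"). But 8.1.2 is the general severity scale, and 11.3 assigns toxicities to the NCI criteria. The missing grade column is mainly an editorial gap.

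**Is the study unable to stop before enrollment ends, or blind to toxicity at 560 mg?** A reader might infer this from 10.1: pooled over 12, more than 50% means 7 DLTs, so 6 of 6 in Part 2 with none in Part 1 would not trigger it. At an assumed common DLT rate of 20%, 30% or 50%, 7 or more of 12 occurs with probability 0.4%, 3.9% or 38.7%. The arithmetic is right, but the documents do not support the inference. Sections 3.3 and 8.3.3 name no time and can act during accrual. Pooling is one unstated reading, and the plan gives no expected DLT rates. Section 7.1.2 calls grade 3-4 events infrequent and independent of dose.

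**Conclusion.** The contradiction in 4.2 holds and needs no outside grading table to show it. It is demonstrated for ANC and platelets only; anemia is not in the table, so no conflict is shown there. It affects Part 1 subjects who continue past two doses: 0 further doses under the text against at most 3 under the table, on scheduled CBCs after a Day 2 finding. The dose count assumes the published visit schedule and no replacement of missed doses. It should be corrected because it is a safety instruction, but nothing in the documents suggests that it has caused harm or is likely to do so often.

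The study-level point is secondary: the rules count different events, and only 10.1 names a time. They can coexist, so this calls for alignment. Whether the 50% is counted per part, and when the first look falls, are the sponsor's design choices and no part of this conclusion.

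**What to change.** 1. In 4.2, add a grade column using the NCI criteria named in 11.3. Discontinue ibrutinib at the first grade 3-4 ANC or platelet count, as the text requires, and delete the TBD restart in those rows.
2. In any milder row that keeps a restart, print the dose in mg.
3. In 4.6, state whether a hold for a milder count is a DLT.
4. Replace 3.3, 8.3.3 and the last sentence of 10.1 with one rule, for example: *The study stops if, at any check during accrual or at target enrollment, more than 50% of subjects evaluated so far have had a DLT or could not complete the protocol because of toxicity or an adverse event.* This keeps the 50% limit and still counts non-completion after a severe challenge reaction. The sponsor should state the denominator and the first look. With no minimum, 1 of 1 already exceeds 50%; with a first look at the fourth subject, 3 of 3 would not act until then.

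**Cost.** A wording amendment with IRB approval (11.5), and no added visits or samples because CBC and CMP are already scheduled on treatment. A Part 1 subject discontinued early gives no information on later doses and is not replaced under 4.6. Checks during accrual may make the next subject wait some days for results, and make an early stop more likely than a single check at target enrollment.
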